### **4.2.2 Subject Evaluation and Statistics**

The Intent-To-Treat (ITT) Population is defined as all subjects who receive at least one dose of any of the study drugs.

The **Per-Protocol (PP) Population for Clinical Efficacy** is defined as all subjects who received at least 75% of the scheduled doses of durvalumab and tremelimumab and at least 4 of the 5 BI 1361849 vaccinations over the first 2 cycles, as well as, respective disease assessments, without major protocol violations.

All efficacy analyses will be based on both ITT and PP populations for each cohort.

Tumor Response will be summarized and analyzed descriptively for each arm and analysis population. A 95% Confidence Interval based on binomial distribution will be constructed for the estimated PFS rate and ORR at 8 and 24 weeks and DCR.

The number and percentage of subjects who died or had a confirmed progression, who survived without a confirmed progression, and who were lost to follow up (unknown survival and/or progression status) will be summarized.

PFS rate at 8 and 24 weeks and the corresponding 95% CIs will be calculated based on Kaplan-Meier product limit estimates and will be displayed along with the corresponding number of subjects at risk.

---

CONFIDENTIAL

PFS and OS will be summarized using the 25th percentile, Median, and 75th percentile as well as the minimum and maximum survival time, calculated by Kaplan-Meier method, and will be displayed graphically.

## 4.3 Biological Activity

### 4.3.1 Endpoints and Assessment Methods

Samples for exploratory assessment of correlative immunologic response will be collected according to the Study Flowchart in Section 3.2. Correlative data will be obtained to assess the effects of the regimen on the tumor microenvironment and biological activity in blood. The exploratory assessments will help to determine whether protein expression, mutational burden, gene expression, soluble PD-L1 or immune cell profiling can be associated with clinical benefit or resistance to combination therapy.

For BI 1361849, cellular and humoral immune response to vaccine target antigens and additional antigens can be assessed to detect signs of antigen spreading (e.g. based on a panel of selected additional NSCLC antigens). NOTE: Per Amendment 9.1, some assessments will no longer be applicable. See Note in Section 4.3.1.2 regarding discontinuation of blood sample collection for immune monitoring.

NOTE: Per Amendment 10.0, all correlative testing will be discontinued, with the possible exception of PD-L1 expression and whole exome sequencing.

#### 4.3.1.1 Tumor Microenvironment

##### Samples:

1. A fresh core pre-treatment biopsy (minimum 3 cores from lung tissue or 4 cores from another site) obtained within 60 days of study start will be requested prior to study entry; archival sample may be used if a pre-treatment fresh biopsy is not feasible.  
NOTE: Per Amendment 9.1, biopsies should not be taken from a target lesion unless that is the only suitable lesion, in which case it should be of reasonable size (refer to Section 5.1, #2).
2. If a fresh core pre-treatment biopsy was obtained, an on-treatment biopsy will be collected 1 week after the 3rd or 5th BI 1361849 treatment, if feasible. This on-treatment biopsy should only be collected if a pre-treatment fresh biopsy was obtained so that paired biopsies may be examined.
3. Optional post-treatment core biopsies (minimum 3 cores from lung tissue or 4 cores from another site) will be obtained at the time of tumor progression or at the completion of treatment from subjects who consent to this procedure and if clinically feasible.
4. If possible and as determined by the Investigator, a minimum of 8 subjects in each arm will have fresh tissue sampling from which fine needle aspiration (FNA) can be also obtained for immune profiling.

A minimum of 25 slides (5 µm formalin-fixed, paraffin embedded (FFPE)) will be requested from the biopsy specimens to evaluate PD-L1 expression as assessed by immunohistochemistry, neoantigen signature and immune biomarker expression in tissue, and to assess the correlation

---

CONFIDENTIAL

of these evaluations with clinical response as well as changes in profiling associated with resistance. Analyses may include the following:

- Mutational burden, gene expression profiling, and immune profiling from before therapy
- Immune markers of response and resistance.

Remaining core biopsies will be formalin-fixed and paraffin-embedded as per institutional standards for further evaluation with immunohistochemistry (IHC) or tumor DNA/RNA extraction for microarrays sequencing or nanostring.

#### **4.3.1.1.1 Immunohistochemistry**

Quantitative immunofluorescence will be used to evaluate multiple immune biomarkers simultaneously in FFPE archival tissue or in biopsy samples, as available.

PD-L1 has been examined in studies of PD-1/PD-L1 inhibitors with mixed results in terms of prevalence and impact on clinical benefit from anti-PD-1/PD-L1 therapy, although this has been attributed to variability in different assays and in different definitions of positivity. It is unknown how the introduction of the vaccine may alter PD-L1 expression and the immune microenvironment and whether that may influence outcomes to combination therapy.

In this study, a pre-treatment biopsy will allow the evaluation of PD-L1 and other immune biomarkers to determine correlation with response to combination therapy. In addition to PD-L1 immunohistochemistry, CD3, CD4 and CD8 immunostaining will be performed to evaluate the degree of immune infiltrate in tumor specimens, as available. Finally, other markers of immune suppression (FoxP3 to stain T regulatory cells, TIM-3, Lag-3 and others) will be evaluated, as feasible.

#### **4.3.1.1.2 DNA sequencing**

Whole-exome sequencing (WES) targeted next-gen sequencing will be performed, as feasible. The targeted sequencing (Oncopanel) is a cancer genomic assay, which is used to detect somatic mutations, copy number variations, and structural variants in tumor DNA that surveys exonic DNA sequences of 275 cancer genes and 91 introns across 30 genes for rearrangement detection.

#### **4.3.1.1.3 Gene expression**

Inflammatory or immune-related gene expression signatures may serve as predictors of clinical benefit and will be evaluated in biopsy samples, as available.

#### **4.3.1.1.4 Immune profiling**

Immune profiling in tumor biopsies will be done to evaluate correlates of response and resistance. FNA samples will also be used, if available.

#### **4.3.1.1.5 Cytokines & Chemokines**

Cytokine and chemokine environment will be determined on protein level in biopsy samples, as available.

---

CONFIDENTIAL

#### 4.3.1.2 Biological Activity in Blood Samples

Blood samples will be collected according to Section 3.2 and may be used for the evaluation of PBMC profile by flow cytometry, cytokine profile, soluble PD-L1 analysis, and exosomal profiling.

**NOTE: Per Amendment 9.1, the following sample collections will be discontinued:**

1. Blood for PaxGene RNA and DNA
2. Blood (PBMC and plasma) for flow cytometry and biological assays
3. Blood for humoral responses and other biomarkers

Blood collection for exosomal profiling will continue as indicated in Section 3.2. Refer to Section 8.1, Amendment 9.1, for rationale.

##### 4.3.1.2.1 Immune Monitoring for Responses to BI 1361849 Vaccine

NOTE: Per Amendment 9.1, these assessments will no longer be applicable. See Note in Section 4.3.1.2 regarding discontinuation of blood sample collection for immune monitoring.

There is a great potential for mutual benefits by combining passive and active cancer vaccine strategies to improve clinical efficiency.

Assays for antigen-specific immune responses encompass, for example, intracellular cytokine staining (ICS) and ELISpot for detection of antigen-specific T-cells by their functional capacity to produce various effector cytokines in response to the vaccine (NY-ESO-1, MageC1, MageC2, 5T4, Survivin, Muc-1) and/or non-vaccine tumor antigens (e.g. MAGE-A3). Humoral responses against vaccine antigens are routinely analyzed by immunoassay techniques such as ELISA and can easily be extended to non-vaccine antigens (antigen arrays). If possible, the immune analyses will also include a detailed phenotypic characterization of, e.g., circulating T-cell subsets, activation and differentiation states of immune cells, and checkpoint marker expression. Furthermore, B cells, NK cells, DCs, monocytes and the peripheral immune-suppressive environment mediated by myeloid derived suppressor cells (MDSCs) and regulatory T-cells are evaluated. Measurements of systemic lymphoid repertoire, e.g., T-cell receptor sequencing and immune-related transcriptional changes, cytokine and chemokine profiling are additional approaches of interest suitable to identify potential blood-derived biomarkers.

Blood samples will be collected according to Section 3.2 for the assessment of humoral and cellular immune responses and additional biomarker screenings. A sample for white blood cell (WBC) count must also be available for the day of the blood samples for immunomonitoring.

Immunomonitoring blood sampling is scheduled at  $7 \pm 2$  days after preceding vaccine administration. In the event that, prior to a planned blood sampling time point, the immediately preceding vaccination has to be delayed or omitted, the blood sampling has to be delayed in the same fashion to ensure that the blood sample has been obtained within  $7 \pm 2$  days (5-9 day time frame) after the immediately preceding vaccination. In the event that the vaccination had to be omitted, blood sampling should occur after the next subsequent vaccine administration.

See Section 8.4 for maximum allowable delays for vaccine administrations.

---

CONFIDENTIAL

The primary aim of these specific immunomonitoring assessments is to trace the immunological effects of the vaccine in regard to *antigen-specific immune responses*, which may be more pronounced under conditions of simultaneous checkpoint inhibition.

Specifically, the aims are:

- to compare vaccine-induced antigen-specific responses, under conditions of simultaneous checkpoint inhibition, with immune-reactivity under checkpoint-blockade alone (cellular and humoral immune responses against vaccine encoded antigens may increase to some extent in context of a general, non-specific immune activation by checkpoint inhibition).
- to generate hypotheses with regards to combination therapy-related biomarker candidates based on comparative immune analysis within a comprehensive data set.

#### 4.3.2 Subject Evaluation and Statistics

NOTE: Per Amendment 9.1, some assessments will no longer be applicable. See Note in Section 4.3.1.2 regarding discontinuation of blood sample collection for immune monitoring.

NOTE: Per Amendment 10.0, all correlative testing will be discontinued, with the possible exception of PD-L1 expression and whole exome sequencing.

For each arm of the study, only subjects who receive at least 1 dose of the respective drugs and who provide the baseline and at least 1 on-treatment sample (if applicable) will be evaluated. As these analyses represent exploratory evaluations of potential biomarkers of response or resistance to therapy, descriptive statistics will be used to describe findings and potential relationships to outcomes to therapy. Criteria for assay positivity (changes compared to baseline) of individual assays will be described in the statistical analysis plan (SAP).

The exploratory pharmacodynamic assessment of the immunologic changes in the tumor microenvironment will include the correlation between clinical activity and the expression level of PD-L1 and tumor-infiltrating lymphocyte (TILs) changes in biopsy samples, as available. The association between response and PD-L1 expression within each arm will be assessed descriptively. Confidence intervals for the overall odds ratio and the odds ratio within each arm will be presented. The association between response and TILs changes (increase, decrease, or no change) will be evaluated similarly.

Subjects are considered fully evaluable for immune response if the following criteria are met:

- Subjects have received at least 4 treatments with BI 1361849 including all vaccine antigens according to protocol
- Samples from baseline and both post-baseline sample 7 days ( $\pm 2$  days) after treatment are available
- Subjects have not received any prohibited concomitant treatments (see Section 5.3.1) within 21 days before on-treatment blood sampling. Immunosuppressive medication that has been taken by subjects 2 to 3 weeks prior to randomization will be documented so that any potential influence on baseline values may be evaluated.
- Sufficient amount and quality of blood sample and isolated PBMCs is available to fully perform and analyze, in accordance with respective assay SOPs, at least the ICS assay, as a measure for antigen-specific cellular immune response

---

CONFIDENTIAL

- The analysis of antigen-specific cell-mediated immune response by ICS is required to include all BI 1361849 antigens including baseline values to be fully evaluable.

All other exploratory results will be summarized descriptively.

---

CONFIDENTIAL

## 5 Subject Eligibility

NOTE: Standard of Care procedures may be used for eligibility assessments provided they meet the criteria specified in either the inclusion criteria or flowchart.

### 5.1 Inclusion Criteria

Eligible subjects ***must fulfill*** all of the following criteria:

1.	
Histologic confirmation of metastatic NSCLC.            For subjects with known EGFR or ALK/ROS-1 mutations, prior therapy must have included an EGFR tyrosine kinase inhibitor or ALK/ROS-1 inhibitor, respectively.            Subjects may have had 1 prior line of anti-PD-1/PD-L1 therapy. Subjects who received prior anti-PD-1/PD-L1 therapy must have progressed during or after treatment, but not prior to Week 12 of treatment.
																
2.	
Measurable disease according to RECIST 1.1, defined as <math>\geq 1</math> lesion that can be accurately measured in at least 1 dimension (longest diameter to be recorded for non-lymph node lesions, shortest diameter to be recorded for lymph node lesions). Each lesion must be <math>\geq 10</math> mm when measured by CT, MRI, or caliper measurement by clinical examination or <math>\geq 20</math> mm when measured by chest x-ray.             NOTE: Per Amendment 9.1, biopsies should not be taken from a target lesion unless that is the only suitable lesion, in which case it should be of reasonable size (refer to Section 4.3.1.1).
																
3.	
Willing to undergo a pre-treatment biopsy, or if not feasible, availability of archival (diagnostic) specimens.
																
4.	
Subjects with treated brain metastases must have been treated with surgery and/or radiation therapy <math>\geq 21</math> days pre-study and must be clinically stable with no requirement for steroids.
																
5.	
Laboratory parameters for vital functions should be in the normal range. Laboratory abnormalities that are not clinically significant are generally permitted, except for the following laboratory parameters, which must be within the ranges specified, regardless of clinical significance:
 
 
 Hemoglobin	<math>\geq 9</math> g/dL	
 
 Neutrophil count	<math>\geq 1.5 \times 10^9/L</math>	
 
 Lymphocyte count	<math>\geq 400</math> cells/<math>\mu L</math>. (See Section 3.3 for instructions for blood draws for PBMC collection.)	
 
 Platelet count	<math>\geq 100,000/mm^3</math>	
 
 Serum creatinine, or Creatinine Clearance	<math>\leq 1.5 \times</math> Institutional Upper Limit of Normal (ULN), or <math>> 40</math> mL/min (by Cockcroft-Gault formula)	
 
 Serum bilirubin	<math>\leq 1.5 \times</math> ULN (except for subjects with Gilbert's syndrome who will be allowed after consultation with their physician)	
 
 AST/ALT	<math>\leq 2.5 \times</math> ULN	
 
 Alkaline phosphatase	<math>\leq 2.5 \times</math> ULN	
 
	Hemoglobin	$\geq 9$ g/dL	Neutrophil count	$\geq 1.5 \times 10^9/L$	Lymphocyte count	$\geq 400$ cells/ $\mu L$ . (See Section 3.3 for instructions for blood draws for PBMC collection.)	Platelet count	$\geq 100,000/mm^3$	Serum creatinine, or Creatinine Clearance	$\leq 1.5 \times$ Institutional Upper Limit of Normal (ULN), or $> 40$ mL/min (by Cockcroft-Gault formula)	Serum bilirubin	$\leq 1.5 \times$ ULN (except for subjects with Gilbert's syndrome who will be allowed after consultation with their physician)	AST/ALT	$\leq 2.5 \times$ ULN	Alkaline phosphatase	$\leq 2.5 \times$ ULN
Hemoglobin	$\geq 9$ g/dL																
Neutrophil count	$\geq 1.5 \times 10^9/L$																
Lymphocyte count	$\geq 400$ cells/ $\mu L$ . (See Section 3.3 for instructions for blood draws for PBMC collection.)																
Platelet count	$\geq 100,000/mm^3$																
Serum creatinine, or Creatinine Clearance	$\leq 1.5 \times$ Institutional Upper Limit of Normal (ULN), or $> 40$ mL/min (by Cockcroft-Gault formula)																
Serum bilirubin	$\leq 1.5 \times$ ULN (except for subjects with Gilbert's syndrome who will be allowed after consultation with their physician)																
AST/ALT	$\leq 2.5 \times$ ULN																
Alkaline phosphatase	$\leq 2.5 \times$ ULN																
6.	
ECOG Performance Status <math>\leq 2</math>.
																

CONFIDENTIAL

7.	Age ≥ 18 years.
8.	Able and willing to provide valid written informed consent.
9.	Subject is willing and able to comply with the protocol for the duration of the study including undergoing treatment and scheduled visits and examinations including follow up.
10.	Body weight > 30 kg.

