#### I. Disease Parameters for RECIST 1.1

Changes in the largest diameter (unidimensional measurement) of the tumor lesions and the shortest diameter in the case of malignant lymph nodes are used in the RECIST 1.1 criteria.

Measurable disease. Measurable lesions are defined as those that can be accurately measured in at least one dimension (longest diameter to be recorded) as  $\geq 20$  mm by chest x-ray, as  $\geq 10$  mm with CT scan, or  $\geq 10$  mm with calipers by clinical exam. All tumor measurements must be recorded in millimeters (or decimal fractions of centimeters).

Note: Tumor lesions that are situated in a previously irradiated area might or might not be considered measurable. *If the investigator thinks it appropriate to include them, the conditions under which such lesions should be considered must be defined in the protocol.*

**NOTE for irRECIST: During target lesion selection the radiologist will consider information on the anatomical sites of previous intervention (e.g. previous irradiation, RF-ablation, TACE, surgery, etc.). Lesions undergoing prior intervention will not be selected as target lesions unless there has been a demonstration of progress in the lesion.**

CONFIDENTIAL

Malignant lymph nodes. To be considered pathologically enlarged and measurable, a lymph node must be  $\geq 15$  mm in short axis when assessed by CT scan (CT scan slice thickness recommended to be no greater than 5 mm). At baseline and in follow-up, only the short axis will be measured and followed.

Non-measurable disease. All other lesions (or sites of disease), including small lesions (longest diameter  $< 10$  mm or pathological lymph nodes with  $\geq 10$  to  $< 15$  mm short axis), are considered non-measurable disease. Bone lesions, leptomeningeal disease, ascites, pleural/pericardial effusions, lymphangitis cutis/pulmonitis, inflammatory breast disease, and abdominal masses (not followed by CT or MRI), are considered as non-measurable.

Note: Cystic lesions that meet the criteria for radiographically defined simple cysts should not be considered as malignant lesions (neither measurable nor non-measurable) since they are, by definition, simple cysts. 'Cystic lesions' thought to represent cystic metastases can be considered as measurable lesions, if they meet the definition of measurability described above. However, if non-cystic lesions are present in the same subject, these are preferred for selection as target lesions.

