**NOTE for irRECIST:**

**Lesions that are partially cystic or necrotic can be selected as target lesions. The longest diameter of such a lesion will be added to the Total Measured Tumor Burden (TMTB) of all target lesions at baseline. If other lesions with a non-liquid/non-necrotic component are present, those should be preferred.**

**Brain lesions detected on brain scans can be considered as both target or non-target lesions depending on the protocol definition.**

Target lesions. All measurable lesions up to a maximum of 2 lesions per organ and 5 lesions in total, representative of all involved organs, should be identified as target lesions and recorded and measured at baseline. Target lesions should be selected on the basis of their size (lesions with the longest diameter), be representative of all involved organs, but in addition should be those that lend themselves to reproducible repeated measurements. It may be the case that, on occasion, the largest lesion does not lend itself to reproducible measurement in which circumstance the next largest lesion which can be measured reproducibly should be selected. A sum of the diameters (longest for non-nodal lesions, short axis for nodal lesions) for all target lesions will be calculated and reported as the baseline sum diameters. If lymph nodes are to be included in the sum, then only the short axis is added into the sum. The baseline sum diameters will be used as reference to further characterize any objective tumor regression in the measurable dimension of the disease.

Non-target lesions. All other lesions (or sites of disease) including any non-measurable as well as measurable lesions over and above the 5 target lesions should be identified as non-target lesions and should also be recorded at baseline. Measurements of these lesions are not required, but the presence, absence, or in rare cases unequivocal progression of each should be noted throughout follow-up.

---

CONFIDENTIAL

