### I. Baseline Assessments in irRECIST

In irRECIST, baseline assessment and measurement of measurable/non-measurable and target/non-target lesions and lymph nodes are in line with RECIST 1.1. One new definition is added: If a subject has no measurable and no non-measurable disease at baseline the radiologist will assign 'No Disease' (irND) as the overall tumor assessment for any available follow-up time points unless new measurable lesions are identified and contribute to the total measured tumor burden (TMTB). irND is a valid assessment in studies with adjuvant setting where the protocol and study design allow the inclusion of subjects with no visible disease.

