### II Follow-up Assessments in irRECIST

#### *A. Follow-up recording of target and new measurable lesions*

**A key difference in irRECIST is that the appearance new lesions does not automatically indicate progression. Instead, all measured lesions (baseline-selected target lesions and new measurable lesions) are combined into the total measured tumor burden (TMTB) at follow up. Baseline-selected target lesions and new measurable lesions are NOT assessed separately. Measurements of those lesions are combined into the TMTB, and one combined assessment provided.**

In order to be selected as new measurable lesions ( $\leq 2$  lesions per organ,  $\leq 5$  lesions total, per time point), new lesions must meet criteria as defined for baseline target lesion selection and meet the same minimum size requirements of 10 mm in long diameter and minimum 15 mm in short axis for new measurable lymph nodes. New measurable lesions should be prioritized according to size, and the largest lesions elected as new measured lesions.

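### Inclusion criterion 2 accepts a 10 mm lymph node on CT or MRI, but Section 8.5 treats a node under 15 mm as non-measurable, so a subject with no valid target lesion can enter

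*Protocol*

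**What the plan says.** **Eligibility (Protocol 5.1, criterion 2).** The criterion opens "Measurable disease according to RECIST 1.1, defined as" at least one accurately measurable lesion. Nodes are mentioned by name: "shortest diameter to be recorded for lymph node lesions". Each lesion must then be at least 10 "mm when measured by CT, MRI, or caliper measurement by clinical examination or" at least 20 mm on chest x-ray. No separate size is given for nodes.

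**Response criteria (Protocol 8.5, RECIST 1.1, part I).** "To be considered pathologically enlarged and measurable, a lymph node must be" at least 15 mm in short axis on CT. Nodes of 10 to under 15 "mm short axis), are considered non-measurable disease". Target lesions come only from measurable disease: "All measurable lesions up to a maximum of 2 lesions per organ and 5 lesions in total".

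**Clinical lesions (Protocol 8.5, RECIST 1.1, part II).** Superficial lesions, with palpable nodes given as an example, are measurable from 10 mm by calipers.

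**irRECIST (Protocol 8.5).** At baseline, "target/non-target lesions and lymph nodes are in line with RECIST 1.1". For follow-up it repeats the nodal limit: "minimum 15 mm in short axis for new measurable lymph nodes".

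**Analysis.** ORR, best overall response, DCR and DoR are secondary endpoints (Protocol 4). The ITT population is all treated subjects, and neither it nor the efficacy per-protocol population requires measurable disease (Protocol 4.2.2; SAP 4.1, 4.2). SAP 7.1 tabulates CR, PR, SD, PD and Not Evaluable. SAP 7.3 counts SD, PR and CR towards DCR.

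**The concern.** Eligibility and response assessment use different size limits for the same node. A screener applying criterion 2 to a 12 mm node on CT finds the subject eligible. A reader applying Section 8.5 to the same scan finds no measurable disease. If there is no other measurable lesion, the subject enters a trial with response endpoints but has nothing from which a target sum can be formed.

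Two things are at stake. One is how that subject counts in ORR, best overall response and DCR, which the SAP does not settle. The other is consistency between sites: the recorded result depends on which section the site follows.

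**Working it through.** The plan states no figure that depends on this point, so there is nothing to reproduce. The check sets the rules side by side and then works out the size of the effect.

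**1. Where the rules differ, for a node of 10 to under 15 mm in short axis**

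| Modality | Criterion 2 | Section 8.5 | Conflict |
|---|---|---|---|
| CT | Qualifies (10 mm) | Non-measurable (15 mm needed) | Yes |
| MRI | Qualifies (10 mm) | Non-measurable: the class of 10 to under 15 mm nodes names no modality | Yes, on that reading |
| Caliper, palpable node | Qualifies (10 mm) | Measurable from 10 mm | No |

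**2. What Section 8.5 allows when there is no target lesion**

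- RECIST 1.1: the non-measurable-disease table offers CR, Non-CR/non-PD, not evaluated or PD. It has no PR, and its footnote advises against using SD.
- irRECIST: irCR and irPD remain. The residual category is irNN, although the wording for irSD would also fit. irPR against the baseline total measured tumor burden is impossible. It becomes possible only if new measurable lesions appear, are called irPD and serve as a new baseline.
- SAP: neither Non-CR/non-PD nor irNN appears in SAP 7.1, and SAP 7.3 does not say whether they count as disease control.

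**3. If the site measures the node as a target anyway**

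PR needs a diameter of at most 0.7 × d, where d is the baseline short axis. Nodal CR needs less than 10 mm, a shrinkage of more than (d − 10)/d.

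| d (mm) | PR at or below (mm) | Shrinkage for nodal CR | Reached first |
|---|---|---|---|
| 10 | 7.0 | any | CR |
| 12 | 8.4 | > 16.7% | CR |
| 14 | 9.8 | > 28.6% | CR |
| 15 | 10.5 | > 33.3% | PR |

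The order switches at d = 10 / 0.7 = 14.3 mm. Below that, the node passes the CR size on less than the 30% shrinkage PR demands. In the RECIST 1.1 table for measurable disease, target CR with persisting non-target disease is scored PR, which counts in ORR. Handled under the non-measurable table, the same scans give Non-CR/non-PD.

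**4. Size of the dilution when Section 8.5 is followed**

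Inputs: 20 subjects per arm (Protocol 3.1.6). ORR of 27% among subjects with target lesions is an assumption, borrowed from the durvalumab plus tremelimumab NSCLC study in Protocol 1.2.1. That rate includes unconfirmed responses, whereas SAP 7.2 requires confirmation. The number affected per arm, m, is assumed to be 0 to 2, with no CR among them.

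Expected ORR = 0.27 × (20 − m) / 20

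- m = 0: 27.0%
- m = 1: 0.27 × 19/20 = 25.65%, a fall of 1.35 points
- m = 2: 0.27 × 18/20 = 24.3%, a fall of 2.7 points

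For comparison, the protocol's own exact 95% interval for 5/20 runs from 8.7% to 49.1%.

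**The case against.** The strongest reply is that criterion 2 names RECIST 1.1 as its standard, so the nodal rule in Section 8.5 is imported and the 10 mm figure is shorthand. Section 8.5 itself gives a general 10 mm paragraph followed by a separate nodal one. This is a fair reading, and the documents do not show which a site would adopt. It does not remove the conflict, because criterion 2 goes on to supply its own definition, mentions nodes, and applies one number to every lesion. The remark in the irRECIST table that sponsors may consider enrolling subjects without measurable disease does not help either, since criterion 2 requires it.

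Three stronger readings are tempting, and the objection to each stands:

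- *Every node of 10 to under 15 mm is in conflict.* Not so. Palpable nodes measured by caliper are treated alike in both places, and a subject with any other measurable lesion is unaffected.
- *Such a subject is an automatic non-responder.* CR and irCR remain available. PD does too, through unequivocal non-target progression or, under RECIST 1.1, new lesions, so PFS events are still captured. Where the node is measured as a target, the error can favor response.
- *Each such subject costs 5 points of ORR.* One in 20 lowers the ceiling from 100% to 95%. The expected loss at a 27% rate is 1.35 points.

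It is also true that metastatic disease with no other measurable lesion is probably uncommon, and that a late eligibility edit may affect few or no new subjects. Amendment 10.0 ends post-study follow-up on 31 October 2021. Enrollment status is not stated.

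**Conclusion.** The contradiction is real for nodes assessed by CT, and for MRI on the reading in the working table. It can admit a subject for whom RECIST 1.1 PR and baseline-referenced irPR cannot be assigned, and whose likeliest categories the SAP does not accommodate. The direction of bias is not fixed: downward for ORR if Section 8.5 is followed, and possibly upward if the site treats the node as a target.

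The size is modest. Under the stated assumptions (0 to 2 subjects per arm, 27% ORR, no CR among those affected), expected ORR is 27.0%, 25.7% or 24.3%, small beside the sampling uncertainty at n = 20. The documents give no count, and zero is possible. A reader might infer that the main conclusions are at risk. They are not: the primary endpoint is safety, the sample size rests on precision for adverse events, and the affected endpoints are secondary and descriptive.

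**What to change.** **Protocol.** Reconcile criterion 2 with Section 8.5 by stating the nodal threshold by modality: 15 mm in short axis on CT or MRI, and the existing 10 mm caliper rule for palpable nodes.

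**SAP.**

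- List subjects with no baseline target lesion under Section 8.5.
- State how Non-CR/non-PD and irNN count in best overall response, ORR and DCR.
- Show ORR and DCR with and without the listed subjects.

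The SAP steps are useful whatever the enrollment status, and an empty listing settles the matter. The cost is a short edit to criterion 2, which may exclude a few candidates, plus a short SAP rule, one extra listing and one sensitivity table. The sample size does not change.
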